8.6. VISIT WINDOWS

The safety and efficacy data will be analyzed per study visit; the named visit as collected on the CRF will be displayed.

During the course of the study, blood draws and certain laboratory measurements for some subjects were delayed. A subset of subjects also experienced a 'treatment interruption' during which treatment was interrupted due to laboratory findings. Further detail will be provided in the Clinical Study Report. As a result, some study visits to occurred outside the pre-specified visit window. In the case where a scheduled study visit was delayed, the labelled study visit from the raw database will be used.

All unscheduled visit values will be excluded from summary tables but will be included on data listings.

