8.5. MISSING DATA

All available safety, PK and efficacy data will be included in data listings and tabulations. No imputation of missing data is planned for primary and secondary endpoints. Abnormal values for assessments (outliers) will be confirmed during the DRM and the primary analysis may be performed with and without inclusion of outliers.

IMPUTATION OF INCOMPLETE DATES.

An incomplete date is any date for which either the day, month or year is unknown, but all three fields are not unknown. An incomplete date occurs when the exact date an event occurred or ended cannot be obtained from a subject. For many of the analyses, a complete date is necessary in order to determine if the event should be included in the analysis (i.e., if the event is treatment-emergent) or to establish the duration of an event. In such cases, incomplete dates will be imputed.

For purposes of imputation, all events with an incomplete end date are assumed to have ended on or before the day the form was completed. In an effort to minimize bias, the project statistician will impute dates in a systematic, reasonable manner. A list of incomplete and imputed dates will be prepared by the project statistician or statistical programmer(s) and will be submitted for review by the clinical project manager and sponsor.

Syneos Health #1009367

Incomplete/missing start and stop dates will be handled as follows:

Table 8.4.1: Imputation of missing dates

Missing	Imputation
Start day	The start day will be imputed as the first day of the month with the following exception: if the partial date is the same month and year as the date of first dose of double-blind medication, then the partial date will be imputed as the date of first dose of double-blind.
End Day	The end day will be imputed as the last day $(28/29/30/31)$ of the month.
End Day and Month	d The end date will be imputed as the 31st of December or last day of study follow up.

For all other data, all available data will be included in the analyses and will be summarized as far as possible. Unless otherwise specified, there will be no substitution of missing data, i.e., missing data will not be replaced; missing data will be handled as 'missing' in the statistical evaluation.

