11. SAFETY OUTCOMES

All outputs for safety outcomes will be based on the SAF population.

The safety outcomes include dermatological endpoints, vital sign measurements, physical examinations, hematology and chemistry laboratory testing, ECG readings, use of concomitant medications, and incidence, severity and duration of adverse events and TEAEs.

Safety tables will be presented by treatment and overall.

Tables variously organized by preferred terms, system organ class, treatment emergence, treatment relationship, severity and study termination will be presented for AEs, TEAEs, unexpected AEs and SAEs.

Descriptive statistics will be presented by treatment and time for safety laboratory values or in change tables for categorized lab variables (e.g., normal vs. abnormal, present vs. absent). Other safety information (e.g., normality of dermatological endpoints, normality of vital signs, normality of physical examinations, normality of ECG outcomes, concomitant medication usage) will be summarized in tables and medically evaluated.

No inferential statistical testing is planned on the safety data, all data will be summarized and listed only. If any post-hoc inferential testing of any variable seems appropriate, the comparison will be made using an appropriate statistical test.

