11.3. CLINICAL LABORATORY EVALUATIONS

Laboratory tests will be performed at Screening and periodically throughout the clinical trial as described in the schedule of events, Section 4. Only data collected by the central laboratory will be included in the analyses with the exception of the screening safety data. Standard international units will be used for all summaries. Laboratory tests within each category and scheduled visit are given in Table 9.4.1. Data for all visits, scheduled or unscheduled, will be listed.

At least one laboratory measurement obtained subsequent to at least one dose of Study Treatment is required for inclusion in the analysis of each specific parameter. To assess change from baseline, a baseline or screening measurement is also required.

Table 11.3.2: Laboratory Tests and Scheduled Study Visits

Laboratory Category	Laboratory Tests Included	
Hematology	hemoglobin, hematocrit, red blood cell (RBC) count, RBC morphology, white blood cell (WBC) count with differential, mean corpuscular volume (MCV), mean corpuscular hemoglobin (MCH), mean corpuscular hemoglobin concentration (MCHC), and absolute platelet count.	
Chemistry	albumin, alkaline phosphatase (ALP), alanine aminotransferase (ALT; SGPT), aspartate aminotransferase (AST; SGOT), bilirubin (total and direct), blood urea nitrogen (BUN), calcium, carbon dioxide (CO2), chloride, creatinine, creatinine phosphokinase (CPK), glucose, phosphate, potassium, sodium, total protein, and uric acid.	
Urinalysis	bilirubin, glucose, ketones, blood, nitrite, pH, protein, specific gravity, and microscopy (if indicated by macroscopic findings).	
Other	Urine Pregnancy Test for Female Subjects	
Estimated Glomerular Filtration Rate (eGFR)	Adult population (≥ 18 years of age): eGFR will be calculated by the MDRD equation at baseline:	

Syneos Health #1009367

eGFR (mL/min/1.73 m2) = $175 \times (Scr)-1.154 \times (Age)-0.203 \times (0.742 \text{ if female}) \times (1.212 \text{ if African American}) \text{ (Levey 2009)}$	
Pediatric population (3 - < 18 years of age): eGFR will be calculated by the Schwartz equation at baseline:	
eGFR (mL/min/1.73 m ²) = $(0.41 \times \text{Height in cm})$ / Creatinine in mg/dL (Schwartz 2009)	

- Actual (observed) values and changes from baseline in hematology and clinical chemistry laboratory parameters will be summarized by treatment group at each scheduled visit

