- The number and percentage of subjects with laboratory measurements outside of the normal range will also be summarized by treatment group and visit.
- Shift from Baseline at each post-Baseline visit will be provided by treatment group in a 3-by-3 contingency table. Denominators for percentages will be the number of subjects with non-missing data at the specific assessment and baseline.
- Box and Whiskers Plots by visit will be produced for all quantitative hematology and clinical chemistry parameters.
- Actual (observed) values in urinalysis and other laboratory parameters will be summarized by treatment group.
- The number and percentage of subjects with laboratory measurements outside of the normal range will also be summarized by treatment group and visit.
- Incidence of patients that have Potentially Clinically Significant (PCS) values at any post-baseline visit.

All data will be listed.

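### SAP 8.6, applied as written, keeps unscheduled values out of the any-time PCS laboratory incidence in SAP 11.3, so a subject abnormal only at an unscheduled draw is counted as not PCS (minor)

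*SAP*

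**What the plan says.** SAP 8.6 (Visit Windows) analyses safety and efficacy data by nominal visit: "the named visit as collected on the CRF will be displayed". A delayed scheduled visit keeps its label. The section ends with a rule for everything else: "All unscheduled visit values will be excluded from summary tables but will be included on data listings". No type of table is exempted.

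SAP 11.3 (Clinical Laboratory Evaluations) describes the laboratory outputs. Observed values and changes in hematology and chemistry "will be summarized by treatment group at each scheduled visit". A later item is the any-time summary: "Incidence of patients that have Potentially Clinically Significant (PCS) values at any post-baseline visit". On unscheduled data the section says: "Data for all visits, scheduled or unscheduled, will be listed". It does not say whether they enter the PCS count. It also restricts the source: "Only data collected by the central laboratory will be included in the analyses with the exception of the screening safety data".

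Two further sentences bear on the point. SAP 8.5 (Missing Data) says: "All available safety, PK and efficacy data will be included in data listings and tabulations". SAP 11 sets the columns: "Safety tables will be presented by treatment and overall".

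**The concern.** An any-time incidence asks whether a subject ever crossed a threshold after baseline. By-visit tables have a good reason to leave out unscheduled values, which have no column to sit in and would give extra weight to subjects tested more often. That reason does not carry over to an ever/never count. There, leaving out a value can only turn a yes into a no.

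Laboratory findings matter in this trial. SAP 8.6 itself records that treatment was interrupted in a subset of subjects because of them, and protocol 6.15.1 foresees additional draws after a clinically significant result. At stake is whether the PCS row, the one any-time, per-subject laboratory summary described in SAP 11.3, means what a reader of the table will take it to mean.

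**Working it through.** The plan gives no figure to reproduce here. The check is a comparison of the rules, followed by the weight of one subject.

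**Step 1: which rule governs the PCS row.** SAP 8.6 covers all summary tables, and the PCS row is a summary table. SAP 11.3 provides for listing unscheduled laboratory data and is silent on tabulating them, which is consistent with 8.6. Applied literally, the PCS row therefore uses scheduled visits only. Against that, 11.3 limits observed values to scheduled visits in terms, while the PCS item refers to any post-baseline visit. That contrast suggests a wider intent but does not state it.

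**Step 2: which draws are affected.**

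| Draw that gives the PCS value | Counted under 8.6 as written | Counted if 8.6 covers by-visit tables only |
|---|---|---|
| Scheduled, on time | Yes | Yes |
| Scheduled, delayed (keeps its label) | Yes | Yes |
| Repeat draw after a scheduled result that was itself PCS | Subject already counted | Subject already counted |
| Unscheduled, central laboratory, no scheduled PCS value | No | Yes |
| Unscheduled, local laboratory only | No (central-laboratory rule) | No (central-laboratory rule) |

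Only the fourth row changes with the reading of 8.6. The fifth is left out under either reading, by the separate sentence in 11.3.

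**Step 3: weight of one subject.** The group sizes are 6 treated and 3 control (protocol synopsis, Statistical Analysis). For k subjects who are PCS only at an unscheduled central-laboratory draw, in a column of n, the incidence is understated by 100 × k/n points.

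- Drug, n = 6: k = 1 gives 100 × 1/6 = 16.7; k = 2 gives 33.3.
- Vehicle, n = 3: k = 1 gives 100 × 1/3 = 33.3; k = 2 gives 66.7.
- Overall, n = 9: k = 1 gives 100 × 1/9 = 11.1; k = 2 gives 22.2.

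With k = 0 the difference is zero in every column. The documents do not give k. The arithmetic assumes the planned 6:3 split and that every subject has at least one scheduled post-baseline result, so that the denominator is the same under both readings.

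**The case against.** The strongest reply is that the SAP is consistent: 8.6 says list and do not tabulate, and 11.3 says list. The sentence in 8.5 is a weak rival, since it introduces a no-imputation rule and does not address unscheduled visits. On this view the point is a preference for a different rule. Most of this stands. The SAP does state a rule, and 8.5 should not be presented as a direct contradiction of it. What remains is that the stated rule gives a downward-only error in an ever/never safety count, and that the PCS wording reads more widely than the rule allows.

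A second reply is that little is lost. The listings keep every value and can be read subject by subject with about 9 subjects. Protocol 6.15.1 asks for clinically significant results to be reported as adverse events. The DSMB reviews all available safety data (protocol 3.4.1). The condition for starting Part 2 in protocol section 10 is a general absence of safety impairment, not tied to this row. This also stands, and it is why the point is minor. The adverse event route is not a full substitute: it depends on the investigator's judgement of clinical significance, and protocol 9.1.1 keeps some abnormal laboratory findings out of adverse event reporting, so a PCS value need not appear there.

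A reader might infer more: that abnormal results were in fact missed, or that the findings behind the treatment interruptions came from unscheduled draws and so leave the tables. The documents support neither. They show no PCS value found only at an unscheduled draw and do not say at which draws those findings arose.

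A reader might also connect this to Week 4, where SAP Table 4.1.1 marks laboratory testing at a home visit. Protocol Table 1 marks none there, 6.19 lists no blood draw among home-visit procedures, and 6.15.1 places laboratory blood collection at the site. The mismatch is real. That Week 4 results would be labelled unscheduled is conjecture about a CRF that is not in the documents.

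**Conclusion.** The point holds as a minor one. Followed as written, SAP 8.6 makes the any-time PCS incidence in SAP 11.3 a scheduled-visits-only count, and any resulting error in the number of PCS subjects is downward. One affected subject is worth 16.7 points on drug, 33.3 on vehicle and 11.1 overall. How many subjects are affected is unknown and may be none.

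The conclusion rests on the literal wording of 8.6 and the planned group sizes. Two gaps limit it. The SAP text supplied gives no PCS thresholds, and the table index is a spreadsheet that was not available, so a rule stated there cannot be excluded. The evidence does not go beyond this one summary row: it does not show that safety information is lost from the report or that any decision depends on the row.

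**What to change.** 1. In SAP 8.6, limit the exclusion of unscheduled values to by-visit summaries and by-visit shift tables.
2. In SAP 11.3, state that the any-time PCS incidence uses all post-baseline central-laboratory values, scheduled and unscheduled.
3. Footnote that row with two numbers: subjects counted only because of an unscheduled draw, and subjects who were PCS only in a local result left out by the central-laboratory rule.

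The cost is a few sentences and minor programming. No new data are needed, because unscheduled laboratory values are already to be listed. The small downside is that subjects tested more often have more chances to be counted; the footnote makes that visible.

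As a separate point, the Week 4 laboratory entry in SAP Table 4.1.1 should be reconciled with protocol Table 1, 6.15.1 and 6.19. The SAP cites protocol version 5.0, so the first step is to confirm that the protocol text compared here is that version.

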8.7. POOLING OF CENTERS

No investigation of center effects is planned. Data from all centers will be pooled.

Syneos Health #1009367

9. DEMOGRAPHIC, OTHER BASELINE CHARACTERISTICS AND MEDICATION

9.1. SUBJECT DISPOSITION AND WITHDRAWALS

Subject disposition will be summarized by treatment group and overall in terms of the number and percentage of subjects who were randomized, completed the clinical trial and discontinued from the clinical trial.

The number and percentage of subjects prematurely discontinued from the clinical trial and the reasons for discontinuation will be summarized by treatment group and overall. Subjects who are not discontinued from the clinical trial will be considered completers.

The reasons for study discontinuation that will be summarized include: (AE, protocol violation, administrative reasons (e.g., inability to continue, lost to follow up), sponsor termination of study, subject choice, and other.

The number and percentage of subjects with major protocol deviations will be summarized by treatment group for all randomized subjects.

All data will be listed.

9.2. EXPOSURE AND TREATMENT COMPLIANCE

9.2.1. Extent of exposure

The duration of exposure during the treatment period will be expressed as the time in days from the first treatment through to last treatment day (inclusive). This is given by the following formula:

A subset of subjects had a treatment interruption. When study drug was reinstated many of these subjects still received the full course of study medication. To account for these cases, exposure to study drug will be calculated using the following formula:

Duration (days) = (date last double blind dose - date first double blind dose + 1)-Total days 'treatment interruption'.

Duration of exposure, number of doses received and doses delayed, missed or not per protocol will be summarized for the SAF using summary statistics for continuous variables.

Drug exposure in grams, defined as the number of tubes used at each visit converted into grams as 15*number of tubes and %BSA treated for the whole study part and each dosing period (20%, 40-45% and 80-90%) will also be summarized.

9.2.2. Treatment Compliance

Study Treatment compliance (%) will be calculated as the actual number of doses divided by the prescribed number of doses, multiplied by 100 and summarized by treatment group.

These numbers will be determined by the number tubes/day dispensed and returned unused by the patient.

All data will be listed; subjects with a treatment interruption will be flagged in the listing.

9.3. DEMOGRAPHIC AND OTHER BASELINE CHARACTERISTICS

All demographic and baseline characteristic data will be summarized by treatment group using descriptive statistics for all patients for each of the following analysis sets: SAF, m-ITT and PPP.

- Gender, Ethnicity and Race will be summarized by the number and percentage of patients in each category
- Age (years), height (cm) and weight (kg) captured at Screening will be summarized as a continuous variable
- Body Surface Area (m²) at captured at Screening
- Estimated Glomerular Filtration Rate (eGFR, ml/min/BSA)
- Systolic blood pressure (mm Hg)
- Diastolic blood pressure (mm Hg)
- Heart Rate (beats/minute)
- Pulse (beats/min)
- Respiratory Rate (breaths/min)

Unless otherwise stated, percentages will be calculated out of the number of patients in the given Analysis Set

All demographic data will be listed.

Syneos Health #1009367

9.4. MEDICAL HISTORY AND CONCOMITANT DISEASES

Descriptions of medical history and concomitant disease findings prior to the Screening Visit will be coded using Medical Dictionary for Regulatory Activities (MedDRA) version 20.0 or higher. Information related to the following disease types or systems: head, eyes, ears, nose and throat (HEENT), respiratory, neurological, cardiovascular, musculoskeletal, metabolic/endocrine/nutritional, hematopoietic, allergies, abdominal and general appearance.

Medical history, as recorded at Screening, will be summarized for the Safety Population (SAF) by the number and percentage of patients within each system organ class (SOC) and preferred term (PT), by treatment.

A disease or illness reported as medical history without a start date will be included in medical history without a date assigned.

Medical history will be sorted by descending overall frequency, by SOC and PT in the summary table. Medical history data listings will be sorted by treatment, patient number, start date, SOC and PT.

9.5. OTHER BASELINE CHARACTERISTICS

The age of diagnosis of SLS, genotype, and all prior treatments for SLS at screening will be summarized by treatment group using summary statistics. The presence or absence of SLS symptoms, including motor disability in the arms and/or legs, foot deformity, speech disorder, seizures, and photophobia, will be summarized.

9.6. MEDICATION

Previous and concomitant medication will be coded using the World Health Organization Drug Dictionary (WHO-DD). The number and percentage of patients taking prior medications and concomitant medications will be summarized overall by ATC (Anatomical Therapeutic Chemical) Levels 2 and 4, in separate tables, for all patients in the SAF population.

Prior and concomitant medications will be presented in a data listing for all patients in the SAF population.

9.6.1. Prior Medication

Prior medications will be defined as medications documented on the Prior and Concomitant Medications eCRF as having started within 30 days prior to assent/consent and stopped prior to baseline visit.

Syneos Health #1009367

9.6.2. Concomitant Medication

Concomitant medications will be defined as medications documented on the Concomitant Medications eCRF as having started within 30 days prior to assent/ consent and ongoing at the time of or after the first dose of double blind study medication or any new medications started after the first dose of double blind study medication.

Syneos Health #1009367

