6.4 Concomitant Medications

Concomitant medications used 30 days prior to consent/assent to treat any medical conditions will be recorded in the CRF. Any changes in dosage or new medications added must be recorded in the subject's CRF. The Sponsor and Investigator or qualified study personnel will review and evaluate concomitant medication usage on an ongoing basis.

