6.5. SAFETY ENDPOINTS

The safety endpoints include dermatological endpoints, vital sign measurements, physical examinations, hematology and chemistry laboratory testing, ECG readings, use of concomitant medications, and adverse events.

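### SAP 9.6.1 and 9.6.2 sort medicines by start date, so, read literally, a long-term medicine still in use, or one begun between consent and first dose, is neither prior nor concomitant

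*SAP*

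**What the plan says.** **Collection.** Protocol 6.4 says: "Concomitant medications used 30 days prior to consent/assent to treat any medical conditions will be recorded in the CRF". Dose changes and newly added medicines are also to be recorded. The test for recording is use, not start date.

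**Classification.** SAP 9.6.1 defines prior medications as those documented as "having started within 30 days prior to assent/consent and stopped prior to baseline visit". SAP 9.6.2 gives two routes to concomitant status. The first is to be documented "as having started within 30 days prior to assent/ consent and ongoing at the time of or after the first dose". The second covers "any new medications started after the first dose of double blind study medication". Neither section offers another route.

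**Use of the categories.** SAP 9.6 states: "The number and percentage of patients taking prior medications and concomitant medications will be summarized overall by ATC", at Levels 2 and 4, in separate tables for the safety population. It uses the same two terms for the listing. SAP 6.5 names the safety endpoints, and the list ends with "ECG readings, use of concomitant medications, and adverse events".

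**Precedence.** SAP 2 says that its methods replace those in the protocol. SAP 13 lists one change from the protocol, on visit windows.

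**The concern.** A start-date test and a use test give different answers for any medicine that a subject was already taking. A drug begun two years before consent and applied or swallowed every day of the trial is concomitant in the ordinary sense, and protocol 6.4 has it recorded, but neither SAP definition admits it. A programmer who follows SAP 9.6 has no sentence there that brings it back.

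At stake is the completeness of a descriptive table for a named safety endpoint. The table is meant to show what else subjects were taking while exposed to study drug. SAP 8.6 reports that some subjects had treatment interrupted because of laboratory findings, and background medication is the kind of context a reader would want when interpreting them. Efficacy results, adverse-event tables and analysis populations do not depend on these definitions.

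**Working it through.** There is no planned figure to reproduce. The check applies the SAP's date rules literally to test cases and compares the result with what protocol 6.4 collects.

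**Inputs**
- Consent falls in the screening window, Day -7 to Day -1 (protocol Table 1).
- The baseline visit and first dose are both on Day 1.
- Prior (SAP 9.6.1): start date from 30 days before consent up to consent, and stopped before baseline.
- Concomitant, route 1 (SAP 9.6.2): start date in the same window, and ongoing at or after first dose.
- Concomitant, route 2 (SAP 9.6.2): new start after first dose.
- Recorded (protocol 6.4): used in the 30 days before consent, or added later.

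**Results with consent at Day -7**

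| Medicine | Recorded under protocol 6.4 | Class under SAP 9.6 | Class under the proposed wording |
|---|---|---|---|
| Started 2 years before, ongoing | Yes | Neither | Concomitant |
| Started 31 days before consent, ongoing | Yes | Neither | Concomitant |
| Started 30 days before consent, ongoing | Yes | Concomitant | Concomitant |
| Started 2 years before, stopped 10 days before consent | Yes | Neither | Prior |
| Started 10 days before consent, stopped before baseline | Yes | Prior | Prior |
| Started between consent and first dose, ongoing | Yes | Neither | Concomitant |
| Started Day 20 | Yes | Concomitant | Concomitant |

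All seven are recorded, and four of the seven fall in neither SAP category. Rows 2 and 3 differ by one day in start date and by nothing in exposure during the trial.

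**Consent at Day -1.** Rows 1, 2 and 4 are still in neither category. In row 6, the next day after consent is the day of first dose. If a start on that day is treated as after first dose, the medicine counts as new and the gap closes. The consent-to-first-dose gap therefore depends on the length of screening and is at most about a week. The gap for long-term medicines does not depend on it.

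These are constructed cases. They show which kinds of medicine are dropped and do not estimate how often that happens.

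**The case against.** The strongest reply is that the wording is a loose paraphrase of the 30-day look-back and that nothing is really lost. Several parts of it have force.

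- SAP 8.5 says in general terms that all available safety data go into listings and tabulations. SAP 8.1 puts every patient in the listings. SAP 11 promises a summary of concomitant medication use without a start-date limit. This stands as evidence of intent, but a general sentence that conflicts with a specific definition does not repair it.
- The table and listing specifications are in a separate spreadsheet (SAP 16 to 18), so the programming may not follow the literal reading. That cannot be seen from the documents.
- SAP 9.5 separately summarizes prior SLS treatments without a 30-day start limit. That covers part of the prior-treatment gap but not other background medicines.
- Protocol 6.4 governs collection and sets no analysis definition. The point is therefore a mismatch between what is collected and what is classified. It should not be called an undeclared departure from a planned analysis.
- A dose change to a long-term medicine must be recorded. If it is entered as a new record with a new start date, the medicine could be counted. The SAP does not say how such entries are handled.

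A reader might also infer three stronger points that the documents do not support:

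- *Most or nearly all background treatment would be missing.* The documents describe a lifelong disorder with spasticity, and list seizures among the symptoms to be documented. They give no medication histories or start dates.
- *The DSMB would be misled.* Protocol 3.4.1 gives the DSMB all available safety data, and nothing limits it to the SAP 9.6 table.
- *An imbalance between arms would be hidden.* Part 1 has about 9 subjects, 6 active and 3 vehicle, with no inferential safety testing planned. SAP 9.6 describes the summary as overall, while SAP 8.1 and 11 describe safety data by treatment and overall. If it is only overall, it could not show an imbalance under any definition.

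**Conclusion.** The definitions are wrong as written and should be corrected. Three classes of recorded medicine meet neither definition: those started more than 30 days before consent and still taken, long-term medicines stopped shortly before baseline, and those started between consent and first dose. A Part 1 table programmed to the text would omit them. The listing would omit them too if it is filtered by the same terms.

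The consequence is an incomplete descriptive summary of one named safety endpoint. The underlying records remain in the CRF. The number of subjects or medicines affected cannot be determined from the documents and could be anywhere from none to every subject. That long-term background medication is common in this population is plausible, but it is an assumption. The conclusion about the wording does not depend on it.

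**What to change.** Replace the two definitions in SAP 9.6.1 and 9.6.2:

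- Prior: any medication taken within 30 days before consent or later, and stopped before first dose.
- Concomitant: any medication taken on or after first dose, whatever its start date.

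Together these place every medicine recorded under protocol 6.4 in exactly one category, as the last column of the table shows for the seven cases. State also that the SAP 9.6 listing includes every recorded medication, which brings it into line with SAP 8.5.

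The cost is two rewritten sentences, one added sentence and a matching change to the table programs. The data are already collected. If the same definitions are to be reused for Part 2, the change should be carried over.
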